Mindfulness + tDCS to reduce urgency incontinence in women

NCT# 04652869

Study Protocol 9/13/2022

Scientific background

Urinary incontinence, particularly urinary urge incontinence (UUI), is a highly prevalent and costly (\$83 billion/year) disorder among older women. Greater than 50% of UUI-related urgency and leakage may be due to situational incontinence provoked by confrontation with specific contextual triggers or cues (e.g., seeing one's front/garage door, doing dishes). We recently found that women with UUI experience increased urgency and actual leakage when exposed to personal "urge" versus "safe" photographic cues taken from their daily lives. Decades of cue-based research across other disorders has shown that such conditioned responses are rarely attenuated with pharmacologic methods and require cognitive and behavioral retraining. Therefore, new methods are needed to specifically target conditioned factors contributing to UUI, in order to effectively combat this persistent contributor to urgency and leakage and augment the efficacy of current UUI treatments.

We propose to test two new intervention methods to attenuate UUI symptomatology and reactivity to urgency cues among women with situational UUI. These methods include brief mindfulness (MI) and transcranial direct current stimulation (tDCS). Employing our well-tested method to personalize cues, women with situational UUI will create photographic personal "urge" cues, which capture their strongest urgency, and "safe" cues, in which they do not experience urge. Then, we will examine the feasibility, acceptability, participant compliance, and efficacy of using MI and/or tDCS to reduce cue-provoked urgency and/or leakage to these salient personal cues, reduce reaction time on a urinary Stroop test, and decrease multiple UUI outcomes.

Study Objectives:

Aim 1: Assess intervention feasibility, acceptability, and compliance. H1: Feasibility: 85% of all enrolled participants will complete the study, Acceptability: Moderate to high acceptability rating of ≥ 50 (0-100 scale) and Participant compliance: ≥ 75 (0-100 scale) for MI compliance on the self-reported post-study survey.

Aim 2: Examine UUI symptom reduction. H1: Each intervention will lead to a pre-post and pre-follow-up reduction in number of UUI episodes, self-report urgency, and bladder symptom severity (ICIQ-FLUTS). H2: MI + tDCS will lead to the greatest reduction in these UUI symptoms.

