Mindfulness + tDCS to reduce urgency incontinence in women

NCT# 04652869

Primary Outcomes: Data Analysis Plan

9/13/2022

Primary Outcomes: Data Analysis Plan. Prior to hypothesis testing, descriptive statistics and graphic displays will be used to identify outliers, missing data, and patterns of attrition, and to guide transformations and appropriate tests. The primary analyses will be evaluated via mixed model regressions with Bonferroni post-hoc comparisons. Mixed model regression features advantages over traditional regression due to the ability to handle repeated assessments of both predictor variables and outcome variables. For **Aim 1**, We will assess feasibility as >85% study completion, acceptability as a score ≥ 50 on 8-item post-study survey rating (scale 0-100), and mindfulness compliance as an average rating ≥ 75 on the compliance survey (scale 0-100). We will use chi-square to assess attrition differences between groups, and one-way ANOVA to assess differences in acceptability and compliance ratings. For **Aim 2**, mixed model regressions will test the main effects of experimental group (1=MI, 2=tDCS, and 3=MI+tDCS) on ICIQ-FLUTS score (pre, post, and follow-up), UUI episodes, and urgency survey scores (3-day mean score at baseline, last three days before re-test, and last 3-days of follow-up) as dependent variables. Pre-intervention (baseline) levels of each dependent variable will be entered as a covariate in respective regression models. This process will be repeated for **Aim 3**, with separate models evaluating treatment effects on Stroop RT and cue-provoked urgency. For Stroop RT, the primary dependent variable will be post-test minus pre-test change. For cue-provoked urgency, the primary dependent variable will represent a double-difference score of urgency minus safe cues, and post-test minus test.

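### Read literally, Aim 2 uses the baseline score as both outcome and covariate; with a random intercept this shrinks every arm contrast to two thirds of its size

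*SAP*

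**What the plan says.** The relevant text is the Aim 2 part of the SAP's Primary Outcomes: Data Analysis Plan. The protocol's Data Analysis Plan repeats it word for word.

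- **Model class:** "The primary analyses will be evaluated via mixed model regressions with Bonferroni post-hoc comparisons".
- **Tested term:** "mixed model regressions will test the main effects of experimental group", with three arms.
- **Outcomes:** the effect is examined "on ICIQ-FLUTS score (pre, post, and follow-up), UUI episodes, and urgency survey scores (3-day mean score at baseline", and the list continues "last three days before re-test, and last 3-days of follow-up) as dependent variables".
- **Covariate:** the next sentence reads "Pre-intervention (baseline) levels of each dependent variable will be entered as a covariate in respective regression models".

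The pre value is therefore explicitly among the outcome values for ICIQ-FLUTS and the urgency survey. For UUI episodes this is an inference, because no separate windows are given for them. No sentence removes the pre row. No time term, group-by-time term, random effect or covariance structure is named.

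The protocol's Study Objectives give two hypotheses for Aim 2. H1 is within-arm: "Each intervention will lead to a pre-post and pre-follow-up reduction in number of UUI episodes" (with urgency and ICIQ-FLUTS alongside). H2 is between-arm: "MI + tDCS will lead to the greatest reduction in these UUI symptoms".

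**The concern.** On a baseline row the outcome and the covariate are the same number, so after adjustment no arm difference can remain there. A group main effect fitted over three rows averages that built-in zero with the two differences that carry the treatment effect. A woman who leaves after baseline contributes only the uninformative row.

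H2 is about how much more the combined arm improves. Under the literal model, the estimated size of every between-arm difference is too small, and any confidence interval reported with it is centred on the wrong value. Whether the tests suffer as well depends on a time term, which the plan leaves open. H1 predicts a reduction in all arms. Without a time term, that shared change goes into the residual.

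**Working it through.** **Inputs.** From the documents: 60 women randomized 1:1:1, so 60/3 = 20 per arm; three assessment times; baseline as covariate; a group main effect; and a feasibility target that "85% of all enrolled participants will complete the study", so about 15% loss. The documents give no effect size, SD, correlation or covariance structure for Aim 2, so there is no stated figure to reproduce. Assumed: random intercept, unit SD, equal correlations r = 0.3/0.5/0.7, continuous scores. A count model for UUI episodes was not simulated.

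**Algebra (complete data).** Group and baseline are both between-woman terms. With a random intercept, their coefficients therefore equal those from regressing each woman's three-row mean on group and Y0:

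(Y0 + Y1 + Y2)/3 = (1/3)·Y0 + (2/3)·[(Y1 + Y2)/2]

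The first part is fitted exactly by the covariate and adds nothing to the group coefficient. The second part gives 2/3 of the baseline-adjusted post/follow-up contrast. The factor does not depend on effect size, SD, r or a time term. For a true 0.80 SD: (2/3) × 0.80 = 0.53 SD.

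**Effect on the test.** The residual of the three-row mean is also 2/3 of the post/follow-up residual. If the between-woman variance is estimated above zero, the standard error shrinks by the same factor and t is unchanged. In one simulated dataset at r = 0.7, the estimates were −0.350 and −0.525, with t = −2.321 for both.

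If that variance is estimated as zero, the standard error is too large. Take r = 0.5 with no arm difference:

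- Between-woman mean square: 3 × (4/9) × [(1 + r)/2 − r²] = (4/3) × (0.75 − 0.25) = 0.667.
- Within-woman mean square, no common change: 1 − r = 0.5.
- Common change of 1.0 SD with no time term: the means 0, −1, −1 deviate from their average by 2/3, −1/3, −1/3. This adds (4/9 + 1/9 + 1/9)/2 = 0.333, giving 0.833.

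Since 0.833 exceeds 0.667, the variance estimate goes to zero.

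**Simulation.** REML with the variance bounded at zero, 20 per arm, MI+tDCS versus MI, Bonferroni alpha 0.05/3, 2000 trials per setting. Entries are percentages for r = 0.3/0.5/0.7. Coverage is that of the 95% interval for the true post/follow-up effect.

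| Setting (true effect; common reduction) | Power, three rows | Power, post/follow-up rows only | Coverage, three rows |
|---|---|---|---|
| Time term (0.80 SD; 1.0 SD) | 80/86/96 | 81/86/96 | 65/60/46 |
| No time term (0.80; 0) | 80/86/96 | 82/86/96 | 66/59/48 |
| No time term (0.80; 0.5) | 76/82/94 | 81/84/95 | 69/62/50 |
| No time term (0.80; 1.0) | 64/73/87 | 81/86/96 | 78/73/66 |
| No time term (0.40; 1.0) | 13/16/19 | 23/27/34 | about 90–92 |
| 15% lost after baseline, time term (0.80; 1.0) | 71/78/91 | 73/78/92 | 61/53/38 |
| 15% lost after baseline, no time term (0.80; 1.0) | 52/61/76 | 73/78/92 | 76/70/62 |

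- In complete data, the three-row estimate differed from 2/3 of the post/follow-up estimate by at most about 2e-14 in any trial, with or without a time term.
- With a time term, coverage is 87/86/81% at 0.40 SD and 92–93% at 0.20 SD.
- With no time term, a 1.0 SD common reduction and a 0.80 SD effect, the between-woman variance was estimated as zero in about 100% of trials (91–95% with no arm effect). Type I error was 2.4–3.5% at nominal 5%.
- With 3 of 20 per arm lost after baseline, the ratio falls to 0.62–0.63. If half of the leavers still give a post value, it is about 0.64.
- Post/follow-up rows only: no shrinkage, coverage 94–96%.

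**The case against.** The strongest reply is that the parentheses only list assessment times and windows, and that the next sentence then gives baseline its one role, as covariate. The plan goes on to apply the same process to Aim 3, whose outcomes are change scores with no pre row. This reading is possible, and on it there is no error. It is not settled, however. The list is expressly of outcome values, H1 needs the pre values, and Aim 3 names its own outcomes, so it cannot decide the rows for Aim 2.

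Second, the two-thirds factor belongs to a model that the plan does not fully state. It needs a random intercept and no group-by-time term. With a group-by-visit interaction the visit-specific effects are recovered (in a large simulated sample, −1.02 and −1.00 for a true −1). That point stands as a condition, but the plan names only the group main effect.

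Third, the loss of power needs both a missing time term and a sizeable common reduction. At 0.5 SD and a true 0.80 SD it is only about 1 to 6 points. With a time term, or with no common change, it is at most about 2 points. That also stands.

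Fourth, the plan promises tests, not confidence intervals; coverage is poor mainly when the arm effect is large; and the order of the arms is preserved. All of this is correct. It limits the harm but does not remove the error in the estimated size.

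**Conclusion.** The concern holds and should be fixed. Followed literally, the Aim 2 model puts the same number on both sides of the equation and tests a main effect diluted by it. With a random intercept and complete data the dilution is exactly one third of every arm contrast, and slightly more with dropout. Only the random intercept and the main-effect-only model are assumed for that factor.

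With a time term, or with no change common to all arms, the harm is confined to the estimate and any interval reported with it. With no time term and a 1.0 SD reduction in every arm, the complete-data loss of Bonferroni power at 0.80 SD is 17/13/9 points for r = 0.3/0.5/0.7. Those power and coverage figures rest on assumed effects and correlations. For UUI episodes, both the baseline outcome row and the use of a continuous-score model are assumptions.

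**What to change.** State in both the SAP and the protocol which visits are outcome rows, which time terms are fitted, and the covariance structure. Two formulations work:

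1. **For H2**, use post and follow-up as the only outcome rows, with baseline as covariate and group, time and group-by-time terms. Report arm contrasts at each visit and averaged over the two. Estimate the within-arm changes of H1 separately.
2. **One model for both hypotheses:** all three visits as outcomes, no baseline covariate, arms constrained equal at baseline, and group-by-time contrasts.

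If the parentheses were meant only as an assessment schedule, say so.

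The cost is one or two sentences and no new data. The one drawback of the first option is that dropping the pre row means H1 needs its own estimate.

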Sixty women will be recruited from the Pitt+Me online registry, local fliers and through collaboration with multiple community and university resources (see recruitment). Telephone screening will determine initial eligibility. Eligible participants will be invited to [name] laboratory for informed consent, further screening, and a semi-structured interview to identify personal urgency and safe cue environments, of which each participant will take pictures. Participants will then be randomized to one of 3 groups: 1) Mindfulness, 2) tDCS, 3) Mindfulness + tDCS. We will use the SAS® high quality pseudorandom deviate generator (SAS Institute, Cary, NC) to randomize subjects in a 1:1:1 ratio. We will use a blocked randomization scheme to force an approximate balance between the number of subjects in each arm at any point during recruitment. Participants will undergo 4 urgency cue exposure sessions with their assigned intervention. Cue-induced urgency and reaction time to modified Stroop will be assessed at baseline and post-training. Bladder diary and urgency survey will be completed daily throughout the study, and for one-week post-training.

Interventions:

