2) Transcranial Direct Current Stimulation (tDCS): tDCS is a safe, non-invasive method of brain stimulation that **can enhance cortical excitability and help attenuate cue-induced reactivity**. tDCS has become increasingly popular in clinical and neurocognitive research, showing promising efficacy for targeting cue-reactivity to stimuli related to a number of disorders (depression, addiction, anxiety), assisting physical and cognitive recovery secondary to stroke and spinal cord injury²⁶⁻²⁸, and promoting cognitive enhancement in healthy subjects.²⁹

³² Addiction research incorporating tDCS has shown reductions in cue-induced craving in response to drug-related stimuli from baseline to re-test following a single session of tDCS,³³ as well as reductions in cue-induced craving and actual smoking after 3-5 tDCS sessions.³⁴

In anxiety research, reductions in self-reported and physiological reactivity to fear stimuli have been noted after similar tDCS methods³⁵. These effects have been characterized through consideration of the PFC's role in decision-making and cognitive control and are presumed to reflect increased control over cue reactivity following PFC-targeted tDCS. Although effective as a standalone treatment to reduce reactivity, the effects of tDCS are greatly enhanced when stimulation is paired with behavioral training that engages the brain processes that underlie the targeted behavior.³⁶ Thus, we purport that brief mindfulness during urgency-cue exposure is a prime candidate for augmentation with dIPFC-targeted tDCS. Enhancement of excitability in the PFC during mindfulness, which has also been shown to increase dIPFC activation^{3,37,38} and cognitive control³⁹ should lead to greater ability to dynamically recruit cognitive control systems during urgency situations, which will aid in retraining the salience of urgency-related cues.

Inclusion Criteria:

- Ambulatory women aged 40+ years
- Able to differentiate between stress symptoms (cough, laugh, exercise) and urgency symptoms (leakage following sudden strong urge to void that is difficult to defer), and history suggestive of UUI using our detailed incontinence history questionnaires and clinical expertise.
- self-report of 2 leaks/week,
- Self-report of 'sometimes' or 'often' experiencing urgency or leakage in at least 4 of 15 common urgency trigger scenarios
- A bother score ≥ 4 on a situational urgency questionnaire

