completion, acceptability as a score ≥ 50 on 8-item post-study survey rating (scale 0-100), and mindfulness compliance as an average rating ≥ 75 on the compliance survey (scale 0-100). We will use chi-square to assess attrition differences between groups, and one-way ANOVA to assess differences in acceptability and compliance ratings. For **Aim 2**, mixed model regressions will test the main effects of experimental group (1=MI, 2=tDCS, and 3=MI+tDCS) on ICIQ-FLUTS score (pre, post, and follow-up), UUI episodes, and urgency survey scores (3-day mean score at baseline, last three days before re-test, and last 3-days of follow-up) as dependent variables. Pre-intervention (baseline) levels of each dependent variable will be entered as a covariate in respective regression models. This process will be repeated for **Aim 3**, with separate models evaluating treatment effects on Stroop RT and cue-provoked urgency. For Stroop RT, the primary dependent variable will be post-test minus pre-test change. For cue-provoked urgency, the primary dependent variable will represent a double-difference score of urgency minus safe cues, and post-test minus test.

7. Malinowski P. Neural mechanisms of attentional control in mindfulness meditation. *Frontiers in neuroscience*. 2013;7:8.

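### Baseline UUI episodes appear to rest on three diary days, a short window for women who may enter at 2 leaks a week; a 7-day baseline would measure the Aim 2 H1 reductions more precisely

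*SAP*

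**What the plan says.** The protocol's inclusion criteria ask for "self-report of 2 leaks/week". No upper limit is given, the item does not say that only urge leaks count, and no diary confirmation is described.

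Under Study Objectives, Aim 2 H1 states: "Each intervention will lead to a pre-post and pre-follow-up reduction in number of UUI episodes". The SAP (Primary Outcomes: Data Analysis Plan), which the protocol repeats, lists two Aim 2 outcomes after ICIQ-FLUTS, first UUI episodes and then the urgency survey scores, followed by one bracket that gives the windows: "3-day mean score at baseline, last three days before re-test, and last 3-days of follow-up". The model is described as follows: "mixed model regressions will test the main effects of experimental group". On the baseline it says: "Pre-intervention (baseline) levels of each dependent variable will be entered as a covariate in respective regression models".

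On collection, the protocol's Procedures section says: "Bladder diary and urgency survey will be completed daily throughout the study, and for one-week post-training". Three days is thus the analysis window and not the length of the diary. Neither document states how many diary days precede the first session, a minimum recorded episode count at baseline, or how zero baselines are handled.

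**The concern.** Three days is short relative to the entry rate. A woman who leaks twice a week has fewer than one expected episode in the window. If she records none, her later counts can only equal or exceed her baseline. The same 3-day value is the reference for both the pre-post and the pre-follow-up change, and it is also the model covariate. Its sampling error therefore enters every UUI-episode analysis, in arms of about 20 women (60 randomized 1:1:1). At stake are the power to detect the H1 reductions and, to a lesser degree, the usefulness of the covariate in comparing arms.

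**Working it through.** The documents give no power, event-rate or zero-count figure for UUI episodes, so there is no stated figure to reproduce.

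**Inputs from the documents:** entry rate 2 leaks/week; 3-day windows at baseline, before re-test and at the end of follow-up; 60/3 = 20 women per arm. **Assumed:** the distribution of counts, the spread of rates across women, the size of the reduction, and a paired t-test.

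**1. Zero baselines at the entry rate.** The expected 3-day count is 2 × 3/7 = 0.857. Under Poisson, P(0) = exp(−0.857) = 42.4%. Over 7 days, P(0) = exp(−2) = 13.5%.

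Other 3-day assumptions at the same rate:
- leaks on exactly 2 separate days per week: C(5,3)/C(7,3) = 10/35 = 28.6%
- exactly 2 leaks placed independently: (4/7)² = 32.7%
- negative binomial, k = 2: (1 + 0.857/2)⁻² = 49.0%
- negative binomial, k = 1: (1 + 0.857)⁻¹ = 53.8%

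**2. Zero baselines above the entry rate (Poisson).**

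| Leaks/week | P(0), 3 days | P(0), 7 days |
|---|---|---|
| 2 | 42% | 14% |
| 3 | 28% | 5% |
| 7 | 5% | 0.1% |
| 14 | 0.2% | about 0 |

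For rates uniform over 2 to 7 a week, the average is (e^(−6/7) − e^(−3))/(3 − 6/7) = (0.424 − 0.050)/2.143 = 17%. For 2 to 14 a week it is (0.424 − 0.002)/5.143 = 8%, or about 5 of 60 women.

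**3. Noise in the change.** Let μ be a woman's daily rate, with no true change. With a 3-day post window, the within-woman variance of the change is μ/3 + μ/3 for a 3-day baseline and μ/3 + μ/7 for a 7-day baseline. The ratio is (1/3 + 1/7)/(2/3) = 0.71, a cut of 29%.

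**4. Power for a within-arm reduction.** This uses 20,000 simulated arms of 20, Poisson counts and a two-sided paired t-test at 5%, with the post window kept at 3 days.

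| Rates | 50% reduction, 3 → 7 baseline days | 40% reduction, 3 → 7 baseline days |
|---|---|---|
| all at 2/week | 37% → 54% | 24% → 37% |
| uniform 2–7/week | 67% → 84% | 46% → 63% |
| uniform 2–14/week | 89% → 97% | 69% → 85% |

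Figures vary by about a point between simulation runs. With negative binomial counts (k = 2 per window), power for a 50% reduction goes from 28% to 40% at 2/week and from 41% to 51% at 2–7/week.

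**5. The baseline-adjusted group comparison.** Let vb be the between-woman variance of the daily rate and μ now the mean daily rate. Then Var(post) = vb + μ/3 and Var(base) = vb + μ/d for d baseline days. The residual variance is Var(post) × (1 − r²), with r² = vb²/(Var(post) × Var(base)). For gamma-distributed rates with mean 3.5 to 14 a week and CV 0.6 to 0.9, the ratio of residual variances (7 days to 3 days) runs from 0.92 to 0.76.

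At mean 3.5 a week and CV 0.6: μ = 0.5 and vb = (0.6 × 0.5)² = 0.09. The reliability of the baseline, vb/Var(base), rises from 0.09/(0.09 + 0.167) = 0.35 to 0.09/(0.09 + 0.071) = 0.56.

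In simulated power for 20 per arm and a 30% versus 60% reduction (assumed), the gain is about 0 to 7 points: 27% to 28% at 3.5/week with CV 0.6, and 67% to 73% at 14/week with CV 0.9.

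**The case against.** A reader might infer that 42% of the trial will start at zero, or that these women make the H1 reduction undetectable. The documents support neither inference. The 42% needs Poisson counts and a woman exactly at the entry rate, and no baseline leak distribution is given. Women are not selected on their 3-day count, so the 3-day group mean remains an unbiased estimate of the group's rate. A zero record prevents that woman from showing a fall; it does not prevent the arm from showing one.

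Four further objections carry weight.

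- The bracket giving the 3-day windows directly follows the urgency survey scores and may apply only to them. ICIQ-FLUTS has its own bracket, so covering both diary-type outcomes is the more natural reading. On the narrower reading the UUI-episode window is simply not defined.
- The large power gains come from a paired test that the SAP does not name. For the written group comparison the gain is small. It is also largest at high leak rates, where zeros are rare, so it reflects the general benefit of more diary days and not relief of a floor.
- If rates run up to 14 a week, the 3-day baseline already gives about 89% power for a 50% reduction.
- Diary length trades burden against precision in a study whose Aim 1 is feasibility, and UUI episodes are one of three Aim 2 outcomes.

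All four stand as limits on the point. They do not remove it: H1 is a within-arm hypothesis, and precision for it improved in every scenario tested. The plan's general provision for transformations cannot recover information lost by counting over three days.

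**Conclusion.** The point holds as an inexpensive improvement in precision and does not invalidate the analysis. It rests on reading the 3-day windows as applying to UUI episodes and on 2 leaks a week being an admissible entry rate. The zero share is conditional on that rate, and its trial-wide value cannot be derived from the documents. Eligibility counts leaks of any type, so the urge-leak rate at entry could be below 2 a week and the zero share higher.

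The worthwhile gain is for the H1 pre-post and pre-follow-up reductions: about 8 to 17 power points for a 50% reduction across the three Poisson scenarios (97 − 89 = 8; 54 − 37 = 17; 84 − 67 = 17). The H2 group comparison gains little.

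**What to change.** In the protocol and SAP, define baseline UUI episodes as the mean episodes per day over all diary days completed before the first intervention session, with a target of seven. Use that value both as the reference for the pre-post and pre-follow-up changes and as the model covariate. The same sentence settles whether the 3-day windows apply to UUI episodes at baseline. The post-training and follow-up windows need not change for this gain.

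The interval in which women photograph their cue environments, before randomization, offers time for the diary. If more than three pre-intervention days are already kept, using them all costs nothing. Otherwise the cost is up to 7 − 3 = 4 more diary days per woman before training, on a diary that she will keep daily in any case. No visits or participants are added. The added burden is small but could slightly affect the 85% completion target in Aim 1.
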